Procedures. Potential subjects will be identified through the specific recruitment methods described in the below section 11. Prior to enrollment, interested Veterans will be **pre-screened**. Study personnel will conduct a medical record review, including neuropsychological assessment records, to ensure study eligibility. As described in the following sections related to recruitment (Section 9: "Recruitment and Feasibility" and Section 11: "Recruitment"), study personnel will then contact individuals by phone or letter, depending on the specific recruitment method, to answer questions about the study, confirm interest in participation, and to schedule an initial study visit. All eligible participants will then complete an **initial study visit** which will include **informed consent** and **baseline measures** (see **Table 5**); all participants will be carefully screened to ensure their ability to comprehend study procedures, risks and benefits. Participants at the VASDHS site will be offered the opportunity to use a Fitbit to track their physical activity and sleep during the study. (The Fitbit Charge 2 is a non-invasive, water-resistant, wrist-worn device that measures steps taken, distance traveled, heart rate, and sleep quality and stages.) Upon enrollment, we will create a unique login ID and password for each participant to enable us to track their data on the Fitbit website each week of the 8-week intervention; we will upload these data during the weekly group session. When connected to a compatible device (i.e., study computer), data are automatically uploaded to the users' Fitbit accounts. The researchers will bring a study laptop to the groups each week, at which time the researchers will upload participants' data for adherence and assessment purposes. These data will then be "dumped" into and stored on a secure study server. We will also upload their data during their last assessment at 21 weeks; however, participants will be given the option of coming to the VA between the 8 week and 21 week assessment to upload their data so they can get continued summary of their progress each week. The participants will be allowed to keep the device when the study ends and guided through the procedure for establishing a new username and password, thereby terminating the research staff's access to their account. All eligible participants will then be **randomized** to either the ME-CCT or SC group. Randomization tables will be prepared by [name], the study statistician, at the beginning of the study. For each site, groups will be randomly assigned to ME-CCT or SC based on the site's randomization table. New study participants will be allocated to the current group awaiting randomization. Once group membership reaches the minimum of 6, the group will be randomized by [name], who will be blind to membership of each group. Randomization procedures and enrollment for each site will be monitored by [name], and if imbalance occurs at any site, he will recommend the necessary adjustment. Following randomization, participants will receive the **intervention (ME-CCT or SC)** for 8 weeks. To reduce the risk of treatment

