Data analyses will proceed in stages: 1) First, descriptive statistics and exploratory analyses will be used to assess the normality of the data and homogeneity of variance. The continuous outcome data will be transformed if necessary by using an appropriate transformation such as the log transform for skewed long tailed data. Similarly, potential covariates will be summarized with descriptive statistics and graphs to determine the most appropriate way to treat these variables. In addition, the results will be inspected for bias due to dropouts or missing data. 2) Although we don't anticipate any baseline differences, we will compare any differences among groups and sites on baseline measures. Any statistically and clinically significant differences will be controlled for in subsequent analyses by adding the target variables as covariates to the model. 3) We propose to use mixed effects modeling to account for clustering structure of the data (i.e., repeated assessments within an individual, groups, therapists and sites) for main hypotheses testing. The mixed effects approach is more powerful than traditional methods and allows the inclusion of subjects with missing data or those who were terminated early in the study, without relying on data imputation procedures. Two specific forms of the mixed effects models of random regression models (RRM), also known as hierarchical linear models (HLM) or multilevel models, and mixed model analysis of variance (MMANOVA) will be considered. Each outcome variable will be graphed versus time for each subject to evaluate what function of time best describes the data. If the change is linear we will proceed with the HLM structure. If the time pattern is not immediately apparent we will proceed with the MANOVA. 4) We will use the extension of the Pattern-Mixture models [89] which allow subject-to-subject heterogeneity, to assess if there is bias due to drop out or missing data. Furthermore, the randomness of missing data will be examined according to recommended procedures [90], which includes comparing group differences in the primary outcomes of subjects with versus without missing data. Specific plans for testing each hypothesis are below.

H1: Compared to those in SC, participants in ME-CCT will show significant improvements in objective cognitive performance and functional capacity.

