Dependent variables: Neurocognitive composite score (Average z score across subtests in the Neurocognitive Battery detailed in **Table 6**); Functional capacity composite score (Average z score across subtests in the Functional Capacity Battery detailed in **Table 7**). **Independent variables:** Treatment group (2 levels, ME-CCT and SC), and Time (4 levels, Weeks 0, 4, 8, 21). **Statistical Analysis:** We will analyze data on all randomized subjects for whom we have a baseline assessment and at least one post-baseline evaluation. Data will be analyzed by mixed effects model methods [91-93] for linear or non-linear trends based on earlier inspection of data. The mixed effects model method provides an estimate of the individual variability around the population trend, the variability of the individual intercepts (baseline values) and slopes (changes across time), and the correlation between them. A fully saturated treatment X time model will be utilized for inference. Covariance structure will be chosen based on Akaike's Information Criterion (AIC). Random group level treatment effects will also be evaluated for importance based on the model AIC. Denominator degrees of freedom will be calculated using the Kenward-Roger small sample correction. The effects of site, therapist and their interaction with treatment will be included and tested. However, we do not anticipate any significant interactions or main effects of these factors given our balanced study design (equal numbers at each site in each group), our standard training and operating procedures at both sites and with all therapists, and our previous analyses from our similarly-designed study (our CCT for TBI study). In any case, the analysis procedures will include these factors and their interaction effects to avoid allowing site or therapist effects to bias treatment comparisons. If we detect any imbalances between the treatment groups, we will follow the primary analyses above with subsequent analyses considering the imbalances to verify that the conclusions are not affected by the imbalances. Analyses will be conducted within and across nested levels of the study design; this will involve within-subject analyses (comparison of occasions of measurement nested within an individual), as well as between-subject analyses. In addition, any treatment group comparison will be adjusted for subject-specific characteristics, and adjustments for changes in these characteristics over the course of the study can be incorporated into the single-subject analyses. **Power Analysis:** In addition to the procedures described by Hedeker and colleagues [94] for Random Regression Models (the RMASS program provided by Hedeker), we used several standard other methods for power calculation and estimation of needed sample size. We selected the sample size that would provide us with a minimum of 80% power across all hypotheses and their expected effect sizes. We used this method with the following assumptions to estimate required sample size: the mixed design of two groups (ME-CCT and SC) and time (4 levels, weeks 0, 4, 8, 21) where the slope is the dependent measure; alpha-level of .02, nature of the hypothesis (two-sided), dropout rate (up to 20%), autoregressive covariance structure (with correlation between sequential assessments set at .45) of the longitudinal data, medium effect size as a between-group difference increasing linearly from 0 at baseline to .5 SD units at the last time point, various correlations (.2, .5, and .8) between the repeated measures, and various effect sizes from medium to large. We estimated that with a final sample size of 180 participants (216, with a drop-out rate of 20%), the study will have

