
minimum 85% power to yield a statistically significant result for a medium effect size. As is noted in the previous sections, we have found medium to large post-treatment effect sizes for several outcome measures in our previous studies.

H2: Compared to those in SC, participants in ME-CCT will show significant improvements on measures of subjective cognitive complaints, subjective functioning, and collateral measures of everyday functioning.

Dependent variables: Subjective Everyday Functioning Composite Score (average total score across the two Neuro-QOL scales, namely the Applied Cognition Executive Function Scale, and the Applied Cognition General Concern Scale); ECog.

Independent variables: Treatment group (2 levels, ME-CCT and SC), and Time (4 levels, Weeks 0, 4, 8, 21). Statistical Analyses: Data will be analyzed similar to the method described for H1. Power Analyses: Power analyses were conducted similarly to H1, and the study will have 87% power to yield a statistically significant result for a medium effect size for H2. We have found large effects on subjective cognitive/functional complaints in previous studies.

H3: Compared to those in SC, participants in ME-CCT will show increased participation in protective activities, as measured by physical and cognitive activity inventories.

Dependent variables: Cognitive Activity Inventory, CHAMPS Physical Activity Inventory for Older Adults. Independent variables: Treatment group (2 levels, ME-CCT and SC), and Time (4 levels, Weeks 0, 4, 8, 21). Statistical Analyses: Data

will be analyzed similar to the method described for H1. Power Analyses: Power analyses were conducted similarly to H1, except the alpha level was set at .01; the study will have 80% power to yield a statistically significant result for a medium effect size for each dependent measure evaluated through H3.

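### Therapy groups are randomised, but AIC decides whether the model keeps a group-level random effect; if groups differ, type I error rises moderately above the planned level

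*Combined protocol and SAP*

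**What the plan says.** Three places in Section 9 of the combined protocol and SAP bear on this.

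- **Procedures (randomisation).** "For each site, groups will be randomly assigned to ME-CCT or SC based on the site's randomization table". New participants join the group then awaiting allocation, and "Once group membership reaches the minimum of 6, the group will be randomized". The therapy group is therefore the randomised unit.
- **Data analysis plan, stage 3.** The main tests are to use mixed models to "account for clustering structure of the data (i.e., repeated assessments within an individual, groups, therapists and sites".
- **H1, Statistical Analysis.** "Random group level treatment effects will also be evaluated for importance based on the model AIC". For site and therapist the plan is firmer: "the analysis procedures will include these factors and their interaction effects". Kenward-Roger degrees of freedom are specified.

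H2 and H3 take over the H1 method. The H1 power analysis uses a two-sided alpha of .02. The H3 power analysis is the same "except the alpha level was set at .01".

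**The concern.** When groups are randomised, members of a group share an allocation and eight weeks of sessions. Any between-group variance in outcome change adds to the variance of the treatment contrast, whether or not the data show it clearly. The plan makes the random term for the randomised unit conditional on the data, yet fixes the site and therapist terms.

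AIC compares model fit; it does not protect the error rate. With few, small groups it has little power to detect a modest group variance. When it drops the term, the standard error becomes the participant-level one. Kenward-Roger cannot restore group-level degrees of freedom for a term that is no longer in the model. Therapist terms absorb variance between therapists, but not variance between groups led by the same therapist.

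At stake are confidence intervals that are too narrow on average and a false-positive rate above the planned alpha for H1 to H3.

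**Working it through.** **Inputs from the documents.** 216 randomised, 108 per arm; 180 analysed; minimum group size 6; effect 0.5 SD; alpha .02 two-sided (H1) and .01 (H3).

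**Assumptions.** The documents give no ICC, number of groups or number of therapists. Since 6 is a minimum, there are at most 216/6 = 36 groups, or 180/36 = 5 analysed per group. Fewer, larger groups were also tried: 24 (average 180/24 = 7.5 analysed) and 18 (180/18 = 10). The ICC, ρ, is the residual value after site and therapist, from 0 to .20.

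**The plan's own figure.** With 90 independent participants per arm, the expected z is 0.5 × √(90/2) = 3.354. Power is Φ(3.354 − 2.326) = Φ(1.028) = 84.8%, against the stated minimum of 85%. For H3 at alpha .01 the same method gives 78.2%, against 80%. The stated power is therefore reproduced, to within two points, by a calculation without clustering.

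**Model for the check.** Balanced arms and one change score with total variance 1. There are G groups of m, and N = Gm = 180. B and W are the between- and within-group mean squares, on G − 2 and G(m − 1) df, with E(B) = 1 + (m − 1)ρ and E(W) = 1 − ρ. P is the pooled mean square on N − 2 df.

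- True variance of the treatment difference: 4[1 + (m − 1)ρ]/N.
- REML deviance gain from the group term: (N − 2) ln P − (G − 2) ln B − G(m − 1) ln W if B > W, otherwise 0. AIC keeps the term if the gain exceeds 2.
- Term kept: SE = √(4B/N), G − 2 df. Term dropped: SE = √(4P/N), N − 2 df.

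**Check by hand: term never modelled, ρ = .05.** The design effect is 1 + 4 × .05 = 1.20 for 36×5 and 1 + 9 × .05 = 1.45 for 18×10. The critical value 2.326 shrinks to 2.326/√1.20 = 2.12 and 2.326/√1.45 = 1.93. Two-sided error is about .034 and .053; simulation gives .034 and .054.

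**Simulated type I error under the AIC rule, nominal .02** (at least 400,000 trials per setting):

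| Assumed ICC | AIC drops term (36×5) | 36×5 | 24×7.5 | 18×10 |
|---|---|---|---|---|
| 0 | 93% | .019 | .019 | .019 |
| .02 | 86% | .022 | .025 | .027 |
| .05 | 71% | .026 | .030 | .035 |
| .10 | 41% | .028 | .031 | .034 |
| .20 | 7% | .022 | .023 | .024 |

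Inflation is greatest around ICC .05 to .10, where the variance matters but AIC often misses it. Above that range AIC usually keeps the term.

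- **Therapist-by-treatment terms added** (four therapists assumed, each leading both arms): 36×5 gives .027 at ICC .05 and .030 at .10; 18×10 gives .040 and .046.
- **H3 at alpha .01, ICC .05:** .014 (36×5) to .021 (18×10).
- **Term always kept, variance estimate unconstrained:** .020 throughout.
- **Term always kept, variance estimate held at or above zero:** 36×5 gives .013–.015 at ICC 0 and .017–.019 at ICC .05. 18×10 gives .008–.013 at ICC 0, and less with therapist terms.

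**The case against.** **The wording.** The AIC sentence can be read as covering only an added random treatment-effect term, with basic group clustering already secured by stage 3 of the analysis plan. On that reading there is less inflation or none. The text does not settle it. But stage 3 states a general intention, and the H1 sentence is the only operative rule for a group-level term. The two need reconciling on either reading.

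**The layout.** The largest figures come from 18×10. That implies groups of 12 at randomisation, and 54/12 = 4.5 groups per arm per site, which equal groups cannot give. This is fair: 18×10 is a sensitivity case. Groups of 6 (54/6 = 9 per arm per site) and of 9 (54/9 = 6) both fit, and they correspond to the 36×5 and 24×7.5 columns, with peaks of .028 and .031. The four-therapist scenario is also an idealisation, because groups do not divide evenly over its eight cells.

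**The ICC.** It is wholly assumed. At 0 to .02 with 36×5 the error is .019 to .022, practically nominal. This stands, and the conclusion is conditional on it.

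**The model.** The check uses one change contrast in a balanced design, not the planned saturated longitudinal model. AIC retention could differ there in either direction, so the third decimal should not be pressed.

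**The remedy.** Holding the variance at or above zero makes the test conservative, and clearly so at 18×10. That is a cost in power, not a loss of validity, and it should be stated for both layouts.

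**Conclusion.** The concern holds. The therapy group is the randomised unit, and on the plain reading the plan lets AIC remove its random effect from the model that tests treatment. If residual between-group variance is non-zero, type I error exceeds the planned alpha, moderately. At nominal .02 it peaks at about .028 with the maximum of 36 groups (1.4 times nominal) and about .035 with 18 groups (1.75 times). Therapist terms do not remove the excess. There is none at ICC 0 and little at high ICCs. The size rests on assumed ICCs, group layouts and therapist numbers, and on a simplified single-contrast model. The direction does not depend on the particular values. This should be fixed, with medium confidence in the size.

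**What to change.** Replace the AIC sentence in the H1 Statistical Analysis with text such as:

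> A random effect for therapy group, including group-by-time so that it enters the treatment-by-time contrast, is retained in all H1–H3 models regardless of AIC, with Kenward-Roger degrees of freedom. AIC is used only to choose the within-participant covariance structure.

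State also whether the group variance estimate may go negative, which keeps the test at nominal level, or is held at zero, accepting a conservative test. This brings the H1 text into line with stage 3 of the analysis plan.

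Restate power with an assumed group ICC and number of groups. For 0.5 SD at alpha .02 with 180 analysed:

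| Assumed ICC | Analysis | 36×5 | 18×10 |
|---|---|---|---|
| 0 | Term omitted | about 84% | about 84% |
| 0 | Term kept | 79–81% | 73–77% |
| .05 | AIC rule | about 76% | about 66% |
| .05 | Term kept | 72–73% | 58–59% |

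The edit is one sentence. At ICC .05 most of the shortfall from the stated 85% comes from clustering that the power calculation leaves out, not from the fix. The AIC rule's apparent advantage comes with an inflated error rate. Because the retained-term figures at ICC .05 fall below the plan's own 80% minimum, the restated calculation may reopen the sample-size question.

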Our study team recently completed a randomized controlled trial (RCT) that demonstrates the efficacy of our manualized, group-based, 10-week (two hours per week), Compensatory Cognitive Training (CCT) intervention for OEF/OIF Veterans with mild traumatic brain injury (TBI). CCT is a brief, inexpensive, patient centered, and holistic/comprehensive multi-modal behavioral intervention. Because Veterans with mild TBI have cognitive impairments similar to those seen in older Veterans with MCI, we conducted a small pilot study demonstrating the feasibility and acceptability of Motivationally Enhanced CCT (ME-CCT), which is our 8-week revision of CCT specifically adapted for the needs of older Veterans with MCI. In addition to compensatory cognitive training, ME-CCT includes motivational interviewing tools to boost the adoption of lifestyle strategies (e.g., diet, exercise) that improve cognition. Thus, the proposed RCT will extend our research and allow us to evaluate the efficacy of our intervention in a large sample of older Veterans with MCI. We will compare ME-CCT to Goal-Focused Supportive Contact (SC) for 8 weeks, followed by a 3 month follow-up period.

Aim 1: To determine whether ME-CCT is effective for improving objective cognitive performance and functional capacity (co-primary outcomes) in older Veterans with MCI. Hypothesis 1: Compared to those in SC, participants in ME-CCT will show significant improvements in objective cognitive performance and functional capacity.

Aim 2: To determine whether ME-CCT is effective for improving secondary outcomes in older Veterans with MCI. Hypothesis 2: Compared to those in the SC control group, participants in ME-CCT will show significant improvements on measures of subjective cognitive complaints, subjective functioning, and collateral measures of everyday functioning.

Aim 3: To determine whether ME-CCT is effective for increasing modifiable protective factors (i.e., physical exercise and mental exercise) associated with reduced risk for MCI and dementia. Hypothesis 3: Compared to those in SC, participants in ME-CCT will show increased participation in protective activities, as measured by physical and cognitive activity inventories.

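### The 85% power stated for H1 is the power for one co-primary composite; if both must be significant, as H1 is worded, power is about 72–79% for a between-outcome correlation of 0 to 0.8

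*Combined protocol and SAP*

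**What the plan says.** Section 6 (Specific Aims) names two co-primary outcomes under Aim 1. Hypothesis 1 is that, compared with the control group, "participants in ME-CCT will show significant improvements in objective cognitive performance and functional capacity". Section 9 repeats H1 and lists two dependent variables for it, the neurocognitive composite and the functional capacity composite.

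The H1 power analysis states the general target: "We selected the sample size that would provide us with a minimum of 80% power across all hypotheses and their expected effect sizes". Its assumptions include "alpha-level of .02, nature of the hypothesis (two-sided"), a difference reaching 0.5 SD at the last time point, and 180 participants in the final sample. The conclusion for H1 is "minimum 85% power to yield a statistically significant result for a medium effect size".

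H2 and H3 also have two dependent variables each. For H2 the text is "Power analyses were conducted similarly to H1, and the study will have 87% power". For H3 it is "Power analyses were conducted similarly to H1, except the alpha level was set at .01", and the 80% power given there is expressly "for each dependent measure evaluated through H3".

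The documents do not say whether H1 needs one significant composite or two. They give no multiplicity procedure and no correlation between the two composites.

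**The concern.** The power target is stated for hypotheses, but the figures behind it appear to be for single outcomes. H1 joins its two outcomes with an 'and' and labels them co-primary, so its natural reading requires both. The chance of winning on both is lower than the chance of winning on either one named in advance, unless the two results move together perfectly. A reader of Section 9 would take 85% as the chance that the primary hypothesis is supported when the assumed effect is present in both composites. If that chance is really in the 70s, the stated minimum of 80% is not met for the primary hypothesis. In addition, without a stated rule, a result that is positive on only one composite could be called a success or a failure after the data are seen.

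**Working it through.** **Inputs from Section 9.** Final sample 180, allocated 1:1, so n = 90 per arm; difference d = 0.5 SD; two-sided alpha .02 (critical value 2.326); stated H1 power 85%.

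**Input assumed.** r, the correlation between the two test statistics. With complete data this is close to the within-arm correlation between the two composites. The documents do not give it, so it is varied.

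**Step 1: reproduce the stated figure for one outcome.**

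Power = Φ(d·√(n/2) − z) = Φ(0.5 × √45 − 2.326) = Φ(3.354 − 2.326) = Φ(1.028) = 84.8%.

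This matches the stated 85%. The calculation contains one outcome and makes no allowance for a second. For H3 at alpha .01 (critical value 2.576) it gives Φ(3.354 − 2.576) = 78.2%, within two points of the 80% that the plan states per measure. For H2 at .02 it again gives 84.8%, about two points below the stated 87%.

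**Step 2: power for both H1 composites.** Take the plan's 85% for each composite. Φ⁻¹(.85) = 1.036, so the joint power is P(Z₁ < 1.036, Z₂ < 1.036), where Z₁ and Z₂ are standard normal with correlation r. At r = 0 this is .85 × .85 = .7225.

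| r | Power for both composites |
|---|---|
| 0 | 72.3% |
| .3 | 74.2% |
| .5 | 75.8% |
| .7 | 77.8% |
| .8 | 79.1% |
| .86 | 80.1% |
| .9 | 80.8% |

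The 80% line is crossed at r ≈ .86. Starting from the reproduced 84.8% instead of 85%, the joint figures are 71.9% at r = 0 and 78.9% at r = .8, and the crossing is at r ≈ .87.

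**Step 3: the same calculation for H2 and H3.** With 87% per outcome, power for both H2 outcomes is 75.7% (r = 0) to 81.7% (r = .8). With 80% per outcome, power for both H3 outcomes is 64.0% to 72.9%. These show why the H2 and H3 percentages need a label saying what they refer to.

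**Limits of the check.** The match in Step 1 is to a simple two-arm comparison at the last time point. The plan describes a slope model, and a slope calculation with its autoregressive correlation of .45 did not reproduce 85%. Step 2 does not depend on this, because it takes the plan's own 85% as the per-outcome power. It also takes the plan's final sample of 180 as given.

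**The case against.** The strongest reply is that the plan can be read consistently as power per test. H3 says so outright, and the H1 sentence speaks of a single significant result. On that reading no figure has been miscalculated, and 85%, 87% and 80% all meet the minimum outcome by outcome. This stands as an account of how the numbers were obtained. It does not settle what Section 9 says, because the 80% target is attached to hypotheses and H1 names both composites.

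A second reply is that the correlation could be high. The batteries overlap in content: memory and attention tests appear in Table 6, and everyday memory and driving/attention tasks appear in Table 7. A correlation above .86 cannot be excluded, and joint power would then reach 80%. The documents give nothing to support a value that high.

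A third reply is that H1 could be met by either composite. With alpha divided as .01 each, power for at least one composite is 95.2% at r = 0, 90.1% at r = .5 and 85.7% at r = .8, with H1 held at .02. That would be a workable plan, but the documents do not specify it, H1 was powered at .02, and its wording says 'and'.

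A reader might go further and infer that the stated power and alpha levels cannot both hold, because .02 + .02 + .01 = .05 while six outcomes tested at those levels sum to 4 × .02 + 2 × .01 = .10, double the error. The documents do not support this. They nowhere claim a familywise .05 or describe the three levels as a split, and H2's .02 is itself only inferred from the reference to H1. The .10 is an upper bound that pools co-primary, secondary and additional outcomes; with all correlations at .5 the figure is about .079, and at .8 about .054. The H1 pair alone totals at most .04.

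**Conclusion.** The point holds for H1 as worded. The stated 85% is the power for one composite. The power to show improvement on both is about 72% to 79% for r between 0 and .8, which is 6 to 13 percentage points below the stated figure and below the plan's own 80% minimum until r reaches about .86.

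This rests on three assumptions: H1 requires both composites to be significant at two-sided .02; each composite has the 85% power the plan states; and r lies in the range shown. The first is the natural reading of the hypothesis but is not stated as a decision rule. The third is not given in the documents.

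It is a mislabelled power figure together with an unstated success rule. It is not a contradiction between the power and the alpha levels, and it does not show that the type I error is inflated.

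**What to change.** In the H1 analysis section, state that H1 is met only if both composites are significant at two-sided .02. In the power paragraph, label 85% as the power for each composite, and give the power for H1 as the joint figure: about 72–79% for an assumed correlation of 0 to .8, with the assumption shown. Label the 87% for H2 and the 80% for H3 as per-outcome as well, and reword the 80% minimum so that it refers to single outcomes.

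The cost is a less favourable stated power for the primary hypothesis, and a commitment that a result on only one composite does not meet H1. No participants are added and no analysis model changes.

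Testing both composites at .05 and proceeding to H2 and then H3 only if the previous hypothesis is met would raise the joint power at the same sample size. That is an optional design choice with its own trade-offs and is not part of this correction.
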